The Sponsor-Investigator has approved the protocol version dated and confirms hereby to conduct the study according to the protocol, current version of the World Medical Association Declaration of Helsinki, ICH-GCP guidelines, ISO 14155 norm and the local legally applicable requirements.

Sponsor-Investigator:

[name], PhD
Department of Gastroenterology, Hepatopancreatology and Digestive Oncology
Erasme Hospital
[name]

EndoscoPic Submucosal dissection using gel versus glycerol for submucosal injection: a randomized controlled multicentric trial (EPSILON)

Version 1 – dated 21/07/2021

Date Signature

1. Protocol synopsis

Name of Finished Product/device: Orise™ gel	
Title of Study: EndoscoPic Submucosal Dissection using gel versus glycerOl for submucosal iNjection: a randomized controlled multicentric trial (EPSILON)	
Indication: Endoscopic resection by ESD of gastric and rectal superficial lesions	
Study centers: Erasme University Hospital Department of Gastroenterology, Hepatopancreatology and Digestive Oncology [name] Eveangelisches Krankenhaus, Teaching Hospital of Dusseldorf, Department of Internal Medicine [name] Cancer Center, Keio University School of Medicine Division of Research and Development for Minimally Invasive Treatment [name] Memorial Sloan Kettering Cancer Center [name]	
Number on participating Belgian Centers	1
Number of participating international centers	3
Studied period (years): Q2 2021-Q2 2024	Clinical Phase: Prospective, open-label, randomized (1:1), multicentric academic study
Hypotheses: Submucosal injection of ORISE™ gel will shorten ESD procedure duration by improving lesion lifting and reducing the number of per-procedural bleedings.	

EndoscoPic Submucosal Dissection using gel versus glycerOl for submucosal iNjection: a randomized controlled multicentric trial (EPSILON)

Version 1 – dated 21/07/2021

Study Design:

A multicentric, randomized, open label prospective study:

- All subjects with indications of gastric and rectal ESD undergo screening and baseline visit
- Informed consent is obtained when scheduling the ESD procedure
- Randomization is made at the time of the ESD procedure after confirmation of the indication
- ESD is performed using a 25 G needle, a dual-knife-J with glycerol (standard solution) or ORISE™ gel in order to remove the lesion en-bloc. Additional saline injection through the electrosurgical knife will be left at the discretion of the endoscopist
- A follow-up visit is scheduled at 2-4 weeks

Study visits:

- Screening and baseline
- ESD procedure
- Post-treatment follow-up at 2_4 weeks

Number of patients (planned and analyzed): 133 patients by arm with a total of 266

Endpoints :**- Primary:**

- Increase the dissection speed of the ESD procedure (defined as the dissected surface (mm²)/ESD duration (min). The dissected surface is defined as maximal diameter of specimen (mm) x perpendicular minimal diameter of specimen (mm) measured on ex-vivo pinned stretched specimen onto a cork. ESD duration is defined as the time from first submucosal injection to final cut time.

- Secondary:

- Total procedure duration (from scope insertion to scope retrieval) (min)
- Number of per-procedural bleeding (+ severity scale: oozing / severe non pulsating/ severe pulsating)
- total hemostatic time (addition of each hemostasis time for each per-procedural bleeding)
- Need for haemostatic forceps during ESD
- Difficulty of the dissection (scale)
- Amount of submucosal solution (glycerol or gel) used for ESD in ml
- Combined use of saline through the knife during ESD (number and ml)
- Number of needle injection dots during ESD (initially / during ESD)
- Need to adjust electrosurgical settings during ESD
- Clear visualisation of the plane of dissection during ESD (scale) (defined in the protocole)
- Rate of en-bloc dissection (defined as endoscopic resection of the targeted area in one bloc)
- Rate of complete endoscopic resection (defined as endoscopic evaluation of complete removal of the targeted area in the treated organ)
- Quality assessment of the pathological specimen (absolute measure of the depth of resected submucosa on the specimen, rate of clear (horizontal and vertical) margins)

EndoscoPic Submucosal Dissection using gel versus glycerol for submucosal injection: a randomized controlled multicentric trial (EPSILON)

Version 1 – dated 21/07/2021

- Adverse events:
 - Per-procedural (incidence of all adverse technical events during the procedure)
 - Early (clinical and laboratory at 24 h post procedure according to CTCAE v 5.0)
 - Late (clinical at 3 weeks follow-up)

Main criteria for inclusion and exclusion:

- Inclusion:

- Subject ≥18 years of age at the time of informed consent
- Patients must have given written informed consent
- Subjects with documented gastric or rectal lesions with indication of endoscopic removal by ESD, namely:
 - Gastric focal lesion with suspicion of early gastric cancer (low or high grade dysplasia with features of early gastric cancer; adenocarcinoma with morphology of superficial lesion and work-up of superficial lesion)
 - Rectal polyps (adenoma or superficial carcinoma) from 0 to 15 cm from the anal margin; with features being recognized indications of ESD: more than 20mm granular LST, more than 20mm non granular LST, more than 20mm villous or bulging polyps, Paris 0-IIa+IIc lesions, lesions with suspicious pattern (Kudo Vi / JNET 2B), lesions with anal canal involvement.

- Exclusion:

- Subjects who meet any of the following exclusion criteria cannot be enrolled in the study:
 - Gastric and rectal neuroendocrine tumour (NET) with indication of ESD will be excluded
 - Gastric and rectal lesions with indication of ESD but strong fibrosis due to previous partial resection will be excluded
 - Subject is currently enrolled in another confounding research
 - Subjects with any other location of ESD (esophagus, duodenum and colon) will not be included.

Support request: Glycerol or ORISE™ gel will be ordered as other pharmaceuticals by the hospital and billed as locally done in routine practice. A collaborative research agreement between Boston Scientific and Erasme Hospital will be signed.

Procedures: Schedule of assessments in Table 1

Statistical Considerations: Sample size was computed using a two-sided Welch T-Test (groups with unequal variances) using an $\alpha = 0.05$ and a power of 80%.

2. Table of contents

1. Protocol synopsis	4
2. Table of contents	7
3. Ethics.....	9
4. Background and rationale.....	11
5. Study objectives and endpoints.....	12
5.1. Study objectives	12
5.2. Study endpoints	12
5.2.1. Primary.....	12
5.2.2. Secondary	12
6. Study design.....	13
6.1. Study design.....	13
6.2. Sample size and randomization process	13
6.3. Participating centres	14
6.4. Study duration	14
6.5. Study periods	14
6.6. Screening period (Day -15 to day -1)	15
6.7. Treatment period (Day 0-1)	15
6.8. Follow-up	15
6.9. Follow-up for patients who have permanently discontinued the study.....	15
7. Patient selection	15
7.1. Inclusion criteria	16
7.2. Exclusion criteria	16
8. Study procedure	16
8.1. Screening endoscopy	16
8.2. ESD procedure	16
9. Assessments per procedure.....	17
10. Adverse event	18
10.1. Reporting of adverse events (AE), serious adverse events (SAE), serious adverse device effects (SADE), unanticipated serious adverse device effects (USADE).....	18
10.2. Definition and assessment of (serious) adverse events and other safety related events	18
10.2.1. Adverse Event (AE).....	18

EndoscoPic Submucosal Dissection using gel versus glycerol for submucosal injection: a randomized controlled multicentric trial (EPSILON)

Version 1 – dated 21/07/2021

10.2.2. Serious Adverse Event (SAE)	18
10.2.3. Device deficiency	19
10.2.4. Adverse Device Effect (ADE)	19
10.2.5. Serious Adverse Device Effect (SADE)	19
10.2.6. Unanticipated Serious Adverse Device Effect (USADE).....	19
10.3. Causality assessment	19
10.4. Reporting timelines	21
10.5. Periodic safety reporting	22
11. Financing and insurance	22
12. References	22
13. Appendix – figures and tables.....	23

3. Ethics

Study registration

The study will be registered on ClinicalTrial.gov.

Categorization of study

We aim to conduct a prospective randomized, open-label, multicentric academic study comparing endoscopic submucosal dissection (ESD) using ORISE™ gel versus glycerol for submucosal injection. A cooperative research agreement between Erasme hospital (Brussels) and Boston Scientific will be signed.

The Orise™ gel solution has obtained a CE mark on the 13th of November 2018, and is FDA approved. Its intended use remains unchanged as it was registered to use as a submucosal lifting solution for endoscopic resection.

Orise™ gel is a premixed sterile solution, prepared in syringes of 12ml, of gum solubilized in saline and calcium chloride with alimentary blue dye.

Glyceol is a premixed commercially available sterile solution containing 10% glycerol, 5% fructose in saline. Blue Indigo dye is manually added to obtain light blue colour.

Competent Ethics Committee (CEC)

This protocol, any protocol amendments, and other relevant documents are submitted to the Ethics Committee of Erasme Hospital (Brussels), Eveangelisches Krankenhaus hospital (Dusseldorf), Memorial Kettering Sloan Cancer Center (New York City) and Keio Cancer Center (Tokyo) for formal approval to conduct the study. No changes will be made to the protocol without prior CEC approval. Premature study end or interruption of the study will be reported within 15 days. The regular end of the study will be reported to the CEC within 90 days, the final study report will be submitted within one year after study end.

Ethical conduct of the study

The study will be carried out in accordance to the protocol and with principles enunciated in the current version of the Declaration of Helsinki, the guidelines of Good Clinical Practice (GCP). The CEC and regulatory authorities will receive annual safety and interim reports and be informed about study stop/end in agreement with local requirements.

Declaration of interests

There is no intellectual, financial or proprietary conflict of interest to declare by the principal investigator or the co-investigators.

Patient Information and Informed Consent

The investigators will explain to each participant the nature of the study, its purpose, the procedures involved, the expected duration, the potential risks and benefits and any discomfort it may entail. Each participant will be informed that the participation in the study is voluntary and that he/she may withdraw from the study at any time and that withdrawal of consent will not affect his/her subsequent medical assistance and treatment.

The participant must be informed that his/her medical records may be examined by authorised individuals other than their treating physician.

EndoscoPic Submucosal Dissection using gel versus glycerol for submucosal injection: a randomized controlled multicentric trial (EPSILON)

Version 1 – dated 21/07/2021

All participants for the study will be provided a participant information sheet and a consent form describing the study and providing sufficient information for participant to make an informed decision about their participation in the study. The choice will be given to the participant to decide whether to participate.

The patient information sheet and the consent form will be submitted to the CEC and to the competent authority to be reviewed and approved. The formal consent of a participant, using the approved consent form, must be obtained before the participant is submitted to any study procedure.

The participant should read and consider the statement before signing and dating the informed consent form, and should be given a copy of the signed document. The consent form must also be signed and dated by the investigator (or his designee) and it will be retained as part of the study records.

Participant privacy and confidentiality

The investigators affirm and uphold the principle of the participant's right to privacy and that they shall comply with applicable privacy laws. Especially, anonymity of the participants shall be guaranteed when presenting the data at scientific meetings or publishing them in scientific journals. Individual subject medical information obtained as a result of this study is considered confidential and disclosure to third parties is prohibited. Subject confidentiality will be further ensured by utilising subject identification code numbers to correspond to treatment data in the computer files.

For data verification purposes, authorised representatives of the investigator, a competent authority or an ethics committee may require direct access to parts of the medical records relevant to the study, including participants' medical history.

Early termination of the study

The Sponsor-Investigator, the competent authority or the competent ethics committee may terminate the study prematurely according to certain circumstances, for example:

- ethical concerns,
- insufficient participant recruitment,
- when the safety of the participants is doubtful or at risk, respectively,
- alterations in accepted clinical practice that make the continuation of a clinical trial unwise,
- early evidence of benefit or harm of the experimental intervention

In the case of an early termination, the sponsor-investigator will notify the end of the trial to the National Competent Authority of the Member State concerned (FAMHP) immediately and at least within 15 days from when the trial is halted, and clearly explain the reasons. "Premature end" is considered as "early termination".

Declaration of end of trial

End of trial is defined as follows: the date of the last visit of the last patient undergoing the trial. Within 90 days of the end of a clinical trial, the sponsor-investigator shall notify the competent authorities of the Member State (FAMHP) and the Ethics Committee that the clinical trial has ended.

EndoscoPic Submucosal Dissection using gel versus glycerol for submucosal injection: a randomized controlled multicentric trial (EPSILON)

Version 1 – dated 21/07/2021

The sponsor-investigator will make an end of trial declaration using the form published in Volume 10 of Eudralex – the Rules Governing Medicinal Products in the European Union. http://ec.europa.eu/health/files/eudralex/vol-10/declaration_end_trial_form.doc

4. Background and rationale

Superficial gastrointestinal (GI) cancers are defined as lesions limited to the mucosa or submucosa without invading the muscularis propria. With the spread and improvement of the quality of endoscopy, early detection of GI cancers or precancerous lesions is growing. Endoscopic resection has been shown to be an adequate treatment for patients with early GI cancers with no or limited submucosal involvement and no additional risk factors. Most superficial lesions may be treated by endoscopic mucosal resection (EMR), such as subpenduculated/pedunculated and small flat lesions¹. However, this technique is unsuitable for en-bloc resection of lesions larger than 15-20 mm or of non-lifting lesions, as it does not permit adequate histological examination of early cancers. To overcome these limitations, endoscopic submucosal dissection (ESD) has been developed. Firstly described in Japan more than 15 years ago, ESD is progressively gaining more attention in Western countries. The basic technique of ESD involves three steps: injection of fluid into the submucosa to elevate the lesions from the muscle layer, pre-cutting the surrounding mucosa of the lesion and dissection the connective tissue of the submucosa beneath the lesions(Figure 1)². The advantage of ESD over classical mucosectomy is the possibility to remove en-bloc the whole lesion without limits due to the size or poor lifting in case of fibrosis. This leads to improved pathological specimen quality without risk of misinterpretation, such as in the case of positive lateral margins for piece-meal resection, avoiding unnecessary surgery. Furthermore, recurrence rate has been demonstrated in several situations (early gastric cancer, squamous cell carcinoma, colorectal adenoma) to be lower when removing a preneoplastic / early cancerous lesion en-bloc with clear margins compared to piece-meal resection^{3,4,5}. Currently, a niche for selected GI superficial lesions (larger than 15-20 mm, suspected of submucosal invasion or fibrotic content) to be treated by ESD has been proposed by the European Society of Gastrointestinal Endoscopy (ESGE) guidelines⁶.

Different techniques and instruments have been developed in order to facilitate this otherwise challenging procedure. Traditionally, ESD requires the injection of some colloidal solution (glycerol, geloplasma, hydroxyethylstrach, etc.) in the submucosal layer in order to obtain long lifting effect and thus allowing the endoscopist to dissect under the lesion^{7,8}. Over the past 5 years, the injection technique has improved due to the development of jet-knives, allowing to add submucosal lifting agent through the knife, thus diminishing the duration of the procedure by avoiding instrument change via the operating channel. Alternatives to colloid-solution assisted ESD have also been developed: pocket creation method and saline-immersion ESD^{9,10}. These techniques use saline injection as a lifting agent and make use of the favorable effect of buoyancy, which helps counteract the force of gravity, creating a traction effect, which is particularly useful in the context of fibrosis.

EndoscoPic Submucosal Dissection using gel versus glycerol for submucosal injection: a randomized controlled multicentric trial (EPSILON)

Version 1 – dated 21/07/2021

Furthermore saline maintains a thick, fluid-soaked submucosa, reducing the requirement for submucosal injection of lifting solution.

Although described to be more easy and quick, several drawbacks of these two ESD techniques have been described, such as the difficulty to open the pocket at the end of the resection, need to come with the tip of the scope in and out of the pocket to understand the limits of the needed dissection area and need of clear vision under the saline, with troubles in case of per-procedural bleeding.

Recently, other colloidal solutions have arrived on the market, such as gel (ORISE™ gel) in order to improve the lifting during ESD. Our preliminary experience using ORISE™ gel as a lifting solution for ESD was unexpectedly favourable with few per-procedural bleeding (possibly due to the viscosity of the fluid taking more space in the submucosa and reducing blood supply in capillaries during the ESD), quick time and facility. As the spread of ESD is closely associated to its easiness, procedure duration (itself associated to number of procedural bleedings and instruments change through the operating channel) and safety, we sought to study comparatively two submucosal solutions when conducting ESD in a specific population presenting gastric or rectal superficial lesions.

5. Study objectives and endpoints

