6.1. Study design

We aim to conduct an multicentric, open label, prospective randomized (1 :1) academic study comparing the submucosal injection using ORISE™ gel and glycerol in a specific population with superficial GI (pre)neoplastic lesions (see Schedule of assessments in Table 1). Patients will be referred by their gastroenterologist after index gastroscopy/colonoscopy showing a potential superficial (pre)neoplastic lesion.

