6.2. Sample size and randomization

Based on available data of the dissection speed from Erasme, we calculated the dissection speed using the Orise gel and glycerol. These means and standard deviations are shown in the table below.

EndoscoPic Submucosal Dissection using gel versus glycerol for submucosal injection: a randomized controlled multicentric trial (EPSILON)

Version 1 – dated 21/07/2021

	Group Glyceol		Group Gel ORISE		Delta Speed (Gel - Glyceol)	
center	n	Speed (mm ² /min)	n	Speed (mm ² /min)	Speed (mm ² /min)	% of increase
Erasme	31	17.11 ± 18.27	10	22.24 ± 10.26	5.13 ± 4.61	23.06 %

A power analysis was performed using the results above to calculate the sample size. Using a two-sided Welch T-Test (groups with unequal variances) with an $\alpha = 0.05$ and power of 80%, with 1:1 randomization, 133 patients would be required to show a statistically significant difference between the groups. If this hypothesized difference is proven this would be a 23% increase in the speed of dissection. The results will also be stratified by site to see if any differences are observed, this will be performed using a generalized linear model.

A computer-based block randomization scheme will be created using block randomization and stratifying by center and by organ type (stomach/rectum). Data will be collected through a printed CRFs and then anonymized and entered into a central web based secured platform.

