According to randomization, using a 25G needle, the lesion will be lifted with a Glyceol solution with indigo blue dye or ORISE™ gel. Mucosal incision will be performed using Dry Cut mode, (E3 30 watts Erbe VIO 300D, E 3.5 Erbe VIO 3; Tubingen, Germany) and subsequent submucosal dissection using dry cut or swift coagulation mode, (VIO 300 E4 30watts; VIO3 E3.5). After mucosal opening, further lifting during the ESD will be performed using the needle or the tip of the knife pushed into the submucosal space with the Glyceol or ORISE™ gel according to randomization. Added saline injected through the tip of the knife is allowed in both groups (with recorded volume) according to the endoscopists convenience. Visible vessels and bleedings will be coagulated with the knife tip (slowly using swift coag E4 30W or using Forced coag E1 15W) or a 4mm (rectum) or 5mm (stomach) coagulation forceps (Coagrasper, Olympus), using soft coagulation (VIO 300 Effect 5, 50 watts (rectum) / 80 watts (stomach); VIO3 E 5.5). For gastric ESD, 80mg of Intravenous PPI will be given during the procedure and 12h later; at discharge PPI 40mg BID will be given after gastric ESD. After the resection, the specimen will be pinned on a cork (or equivalent) to stretch it moderately and expose the lateral margins. Then, measures of the maximal diameter (mm) and perpendicular minimal diameter will be obtained and recorded by picture capture using the scope. Thereafter, it will be immersed into formaldehyde and sent to the pathologic lab.

Patients will remain hospitalized overnight and a blood test will be performed before their discharge.

9. Assessments per procedure

- Duration of ESD procedure defined as the time of first injection to final cut time
- Total duration of the endoscopic procedure (from endoscope insertion to scope retrieval)
- Calculated speed of the dissection (surface dissected (mm²)/ESD duration (min)).
- Number of per-procedural bleeding (+ severity scale: oozing / severe non pulsating/ severe pulsating)
- Total hemostatic time (addition of each hemostasis time for each per-procedural bleeding)
- Need for haemostatic forceps during ESD
- Difficulty of the dissection (scale)
- Amount of submucosal solution (glycerol or gel) used for ESD in ml

EndoscoPic Submucosal Dissection using gel versus glycerol for submucosal injection: a randomized controlled multicentric trial (EPSILON)

Version 1 – dated 21/07/2021

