3.1.1 Hypotheses

Based on available data of the dissection speed from Erasme, we calculated the dissection speed using the ORISE Gel and glycerol. These means and standard deviations are shown in the table below.

	Group Glyceol		Group Gel ORISE		Delta Speed (Gel - Glyceol)	
center	n	Speed (mm ² /min)	n	Speed (mm ² /min)	Speed (mm ² /min)	% of increase
Erasme	31	17.11 ± 18.27	10	22.24 ± 10.26	5.13 ± 4.61	23.06 %

A power analysis was performed using the results above to calculate the sample size. Using a two-sided Welch T-Test (groups with unequal variances) with an $\alpha = 0.05$ and power of 80%, with 1:1 randomization, 133 patients would be required to show a statistically significant difference between the groups. If this hypothesized difference is proven this would be a 23% increase in the speed of dissection. The results will also be stratified by site to see if any differences are observed, this will be performed using a generalized linear model.

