4.5 Interim Analyses

No formal interim analyses are planned for this study.

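### Does naming early benefit as a reason to end the trial undermine the 5% error rate when no interim analysis is planned?

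*Protocol*

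**What the plan says.** Protocol section 3, under Early termination of the study, says that the sponsor-investigator, the competent authority or the ethics committee "may terminate the study prematurely according to certain circumstances, for example" ethical concerns, poor recruitment, doubts about safety, changes in accepted practice, and "early evidence of benefit or harm of the experimental intervention". After an early stop the sponsor-investigator must notify the national authority "immediately and at least within 15 days from when the trial is halted, and clearly explain the reasons".

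SAP 4.5 reads: "No formal interim analyses are planned for this study". SAP 4.7 requires changes to planned analyses to be written into an amended SAP that is approved before those analyses are run.

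The design calculation is a fixed one. Protocol 6.2 states: "A power analysis was performed using the results above to calculate the sample size". SAP 3.1.1 gives its basis: "Using a two-sided Welch T-Test (groups with unequal variances"), alpha 0.05, power 80%, 133 per arm. The Welch test is named as the basis of the sample size; a generalized linear model by site is also mentioned.

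Protocol 6.1 describes an "open label, prospective randomized (1 :1) academic study". Under Protocol 8.2, after the resection, "measures of the maximal diameter (mm) and perpendicular minimal diameter will be obtained and recorded by picture capture using the scope".

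**The concern.** A stopping ground for benefit normally comes with a rule: when to look, at which endpoint, against what boundary, and by whom. Here there is a ground and no rule. The trial is open label, and both parts of dissection speed (specimen size and ESD duration) are known on the day of the procedure. The sponsor-investigator, who may stop the trial, could in principle see speed by arm as data accrue. SAP 4.5 excludes only *formal* interim analyses, and the section on ethical conduct promises annual interim reports without describing their content.

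If speed were compared repeatedly and the trial stopped when gel looked better, the false-positive rate would exceed 5% and the reported gain would be too large.

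**Working it through.** **1. The plan's own figure.** Inputs (Protocol 6.2, SAP 3.1.1): means 22.24 and 17.11 mm²/min, difference 5.13; SDs 10.26 and 18.27; two-sided alpha 0.05; power 80%.

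- Normal approximation: n = (1.960 + 0.842)² × (18.27² + 10.26²) / 5.13² = 7.849 × 439.06 / 26.317 = 130.9, so 131 per arm.
- Welch test, noncentral t with Satterthwaite degrees of freedom: power is 79.95% at 132 per arm and 80.25% at 133.

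The stated 133 per arm is reproduced. It is a single-analysis figure with no allowance for looks, which agrees with SAP 4.5.

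**2. Error rate of the plan as written.** With one analysis at two-sided 0.05, type I error is 5.0%. A stop caused by evidence from outside the trial leaves it there, because the decision does not depend on the trial's own speed data.

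**3. Error rate if the ground were used on the trial's own data.** The documents give no looks, so everything here is assumed: equally spaced looks, each at nominal two-sided p<0.05, and a final two-sided test at 0.05.

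For one look at half the information, the interim and final z statistics have correlation √0.5 = 0.707. If that look can stop only for gel:

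- P(gel side) = 0.025 + 0.025 − P(both exceed 1.96) = 0.050 − 0.0084 = 0.0416.
- Adding 0.025 on the glycerol side at the end gives 0.0666.

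The mean estimate uses SE = √(439.06/133) = 1.817, an expected final z of 5.13/1.817 = 2.82, and simulation at the planning values.

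| Analyses, final included | Type I error, early stop for gel only | False claims for gel | Type I error, early stop in either direction | Mean estimated gain, gel-only stops (true 5.13) |
|---|---|---|---|---|
| 1 | 5.0% | 2.5% | 5.0% | 5.13 |
| 2 | 6.7% | 4.2% | 8.3% | 5.64 (+10%) |
| 3 | 7.9% | 5.4% | 10.7% | 5.99 (+17%) |
| 4 | 8.8% | 6.3% | 12.6% | 6.24 (+22%) |

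Moving a single either-direction look from 25% to 75% of the information changes its 8.3% to between 9.1% and 7.3%.

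**4. What has to happen for any row below the first to apply.**

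| Needed | What the documents provide |
|---|---|
| A scheduled or triggered comparison by arm | None; SAP 4.5 plans no formal interim analysis |
| A pooled speed dataset by arm in use during the trial | Printed CRFs, anonymized and entered on a central platform (Protocol 6.2); no mid-trial efficacy use described |
| An endpoint and threshold for benefit | None; the clause does not mention speed |
| Authority to add the analysis without review | SAP 4.7 requires an amended SAP approved first |
| A stop that passes unnoticed | Fewer than 266 patients, and reasons owed to the authority |

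The only yearly report that the Protocol describes further is the one in 10.5, which is a safety update. That fits reading the annual reports as safety reporting, although section 3 does not say so.

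**5. Would editing the clause help?** The list is introduced as examples. Removing benefit from it takes away no one's power to stop, and it also drops the outside-evidence ground, which does not inflate the error. If the sponsor later wanted an efficacy look, an amended SAP could add one at almost no cost. With one half-way look and O'Brien-Fleming limits (p 0.0052, then 0.0480), power at 133 per arm is 80.3% against 80.6% without a look (normal approximation).

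**The case for a change.** The best counter-argument is that the safeguards are incomplete. SAP 4.7 governs changes to planned analyses, and an informal look at the accumulating data might not be treated as one. Ethics approval covers protocol changes, but stopping on a ground already listed is not a protocol change. Explaining a stop comes after it and does not restore alpha. The Background reports that early experience with the gel was better than the investigators had expected, so the temptation would lie in one direction. The SAP also refers to a protocol dated November 2020, so the two texts may not have been checked against each other.

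Part of this stands. Neither document bars comparing speed by arm before the end, and a benefit stop on the trial's own data without a prior amendment could not be credited with 5% alpha. But that argues against departing from the plan; it does not show that the plan is wrong. Knowing the allocation of one's own patients is not a pooled four-centre comparison, which would take a deliberate analysis. Nor does the list prescribe such an analysis: it is shared with regulators and ethics committees, whom no SAP wording would bind.

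**Conclusion.** No change follows. This is an unwritten detail that analysts fill sensibly: where no interim analysis is planned, they do not test efficacy before the end, and if they wish to, they amend the SAP first. Followed as written, the plan gives one final analysis, a two-sided error of 5%, and 133 per arm as computed.

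The inflation of 1.7 percentage points (6.7% against 5.0%) for one half-way look, and the larger figures for more looks, rest on assumed looks, an assumed p<0.05 trigger and disregard of SAP 4.5 and 4.7. They also take the Welch test as the primary analysis, which the documents state only as the sample-size basis. A sentence in SAP 4.5 saying that speed is not compared by arm before database lock would do no harm if the SAP were reissued for other reasons, but the validity of the planned analysis does not depend on it. An amendment on this point alone would go to the four centres' ethics committees and would leave the analysis as it is.
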